Randomization. We will randomize patients to the intervention or delayed results arms, controlling for possible bias due to confounding by provider by using a within-provider randomization scheme within each site. Overall, this scheme will balance treatment conditions across known (e.g., primary care versus specialty care) and unknown (e.g., future adherent versus non-adherent status at randomization) provider characteristics. In addition, as we expect the depression severity of patients to be associated with primary versus specialty care status of the providers, stratification will also tend to balance depression severity across the intervention groups. The randomization will be based on a permuted blocks approach, with (slightly) varying block sizes to discourage "guessing" of upcoming allocations [38]. The research coordinator at each site will conduct the randomization, having been trained on the use of the system during the study initiation meeting. Within each site, the system will maintain a log of the participants randomized. Each site will also have a short list of random assignments, one list per consented provider, to be used in the event that there is a system failure at the time of randomization. The list of randomized allocations will be maintained separately from the tracking and research data, to ensure blinded assessments by the interviewers.

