5.6.a Patient response to treatment (Hypothesis #1). The primary outcome measures will be a set of binary indicators of remission (PHQ-9 score \leq 5) across the intervention phase time points (weeks 4, 8, 12, 18 and 24). We will use a mixed effects logistic regression model to test the hypothesis that patients whose treatment is informed by the PGx results are more likely to be in remission than those receiving usual care. The model will have a binary indicator from the intervention group as the main explanatory variable, together with variables for time and group by time effects. The model will also include a fixed effect for site. The covariance structure of the model will take the hierarchical structure of the design into account, to accommodate nesting of repeated measures within patients, and nesting of patients within providers. Including a random intercept for provider, and correlated residuals within patient, should account for the nesting, but we will use information criteria to compare the fit of different covariance structures to ensure adequate fit. As there is particular interest in the remission rate of patients at the end of treatment, we will report a model-based comparison between the groups at the endpoint of the intervention phase.

To examine the effects of patient-level and provider-level characteristics, we will include these variables and their interactions with intervention group in the logistic regression model. For example, we will examine the effects of sex, race and ethnicity, baseline depression severity, the number of prior treatment episodes, and the effects of primary care versus specialty care, etc. We will also test for heterogeneity of the intervention effect across sites (i.e., site by treatment interactions). Analyses to assess the influence of missing data, and of adherence at the provider and patient level, are described below. Our reports will include clear descriptions of the statistical methods used and the clinical interpretations of the parameters used to test the hypotheses, with estimates, standard errors, confidence intervals and *p*-values associated with the parameters.

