5.6.i. Adequacy of sample size. The single primary outcome is a set of repeated binary indicators of remission from depression. As we have a single outcome, we use a Type 1 error rate of 5%. Although we expect the intervention arm to be no less efficacious than the delayed results arm, we use a two-sided test. We also assume a 20% loss to dropout, distributed evenly over time, and across the two groups. The parameters that determine power are the base rate, which is the rate of treatment success expected in the delayed results arm, and the treatment effect. The anticipated remission rate in usual care is based on results from STAR*D [19]. For the base rate, we consider rates of 20-25-30-35%, and for the treatment effect, we look at effects of 5-6-7%. The study design has patients nested within providers, so it is possible that there will be small correlations between the results for two patients of the same provider. Accounting for nesting within provider should also address the nesting within sites [61]. Our design will have approximately 200 providers, with an average of ten patients per provider. The design effect due to provider is then 1+9*r, where r is our assumed provider intra-class correlation. Our sample of size 2000 is then equivalent to an "independent patients" sample of 2000/(1+9*r). We anticipate a low ICC, on the order of r<0.05. If we assume that r=0.05, then the design effect is 1.45, and the effective sample is 1379. For a base rate of 30%, and an assumed within-patient correlation of 0.4 or lower in a compound symmetry structure, then we have 82% power for a 5% treatment effect and 92% for the same effect in an ar(1) structure, with higher power for the same 5% effect with lower base rates. For r=0.01, where we have an effective sample size of 1835, we have power in excess of 90% for 5% effects, under either covariance structure. Even with a conservative estimate of r=0.1, the design effect is 1.9, yielding more than 80% power for treatment effects of 6% or greater.

5.6.j. Data management staffing. [name] and his staff will be responsible to coordinate the various data collection methods used in the clinical trial, and will provide support to the investigators, including site principal investigators to support additional exploratory hypotheses. In this section, we describe the methods that we will use to collect, store, and distribute data from the trial.

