- 4) In the delayed results group, there will be a decrease in the probabilities of antidepressants characterized as red or yellow prescribed in the 30 days after the release of the PGx test results, compared to the 30 days prior to release of results.

Rationale for amendments made– To clarify the intent of Hypothesis #4, it was agreed that this analysis would not be included in the primary paper.

Sample Size and Power Considerations.

We have two primary hypotheses, so we will test each at a 2.5% significance level, using two-sided tests.

The primary outcome for Hypothesis #1 is a set of repeated binary indicators of remission from depression. We assume a 20% loss to followup, distributed evenly over time, and across the two groups. The anticipated remission rate in usual care is based on results from STAR*D [2]. For the base rate, we consider rates of 20-25-30-35%, and for the treatment effect, we look at effects of about 5%. To account for correlations between the results for two patients of the same provider, we assume an intra-class correlation (ICC) of 0.05 or lower for providers, which should also address the nesting within sites [21]. We assume our design will have approximately 200 providers, with an average of ten patients per provider, so the design effect for an ICC of 0.05 is 1.45. For a base rate of 30% (based on results from STAR*D [2]), and an assumed within-patient correlation of 0.4 or lower in a compound symmetry structure, we have 82% power for a 5% treatment effect and 92% power for the same effect in an autoregressive (ar(1)) structure, with higher power for the same 5% effect with lower base rates. For a provider ICC of 0.01, where we have an effective sample size of 1835, we have power in excess of 90% for 5% effects, under either covariance structure.

For Hypothesis #2, the primary outcome is an ordinal response indicating the gene-drug interaction potential (coded as green, yellow, and red based on the PGx test for non, moderate and significant drug- gene interactions) of the initial prescription made during the intervention period. Assuming that the overall proportions in the sample are approximately 40%/40%/20% for green/yellow/red, respectively, then our sample of 2000 provides 80% power to detect a common odds ratio of 1.29 under a proportional odds model, at a significance level of 2.5%.

Data Analysis Plan for the Completed Sample.

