Prior to performing analyses, we will apply standard data-cleaning procedures. Specifically, we (1) screen the data for data-entry errors, (2) check for outliers, (3) assess the extent and pattern of missing data, and (4) check that appropriate assumptions of normality for data distributions are met whenever necessary.

Primary hypotheses.

Patient response to treatment (Hypothesis #1). The primary outcome measures will be a set of binary indicators of remission (PHQ-9 score ≤ 5) across the intervention phase time points (weeks 4, 8, 12, 18, and 24). We will use a mixed-effects logistic regression model to test the hypothesis that patients whose treatment is informed by the PGx results are more likely to be in remission than those receiving usual care. The model will have a binary indicator of intervention group as the main explanatory variable, together with the baseline phq-9 score, and variables for time and group-by-time effects, and a fixed effect for site. To accommodate nesting of repeated measures within patients, and nesting of patients within providers, the models will include a random intercept for provider and correlated residuals within patient; we will use information-criteria comparisons to compare the fit of different covariance structures to ensure adequate fit. As there is particular interest in the remission rate of patients at the end of treatment, we will report on a comparison between the groups at the endpoint of the intervention phase (week 24), based on our final model.

Patient and provider use of PGx results (Hypothesis #2). For each provider-patient dyad in the trial, we will use the results of the PGx battery to classify each antidepressant medication prescribed by the provider to that patient during the study period as green, yellow, or red, thus creating an ordinal measure for each time the provider prescribes a medication. The primary outcome for Hypothesis #2 will be the ordinal variable corresponding to prescriptions written in the first 30 days after randomization. In the case of Veterans having simultaneous prescriptions, we will use a “worst-case” approach, assigning the highest level of the green, yellow and red scale. We will compare the groups on their probabilities of prescriptions of green, yellow, or red using a mixed-effects ordinal regression model, including random intercepts for providers and fixed effects for sites.

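### Hypothesis 1 power uses the design effect for randomizing whole providers (1 + 9r), although patients are randomized within provider; the error is conservative

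*SAP*

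**What the plan says.** Protocol 5.2 (Randomization) allocates patients "using a within-provider randomization scheme within each site", by permuted blocks, with a separate back-up list for each consented provider. Each provider therefore contributes patients to both arms.

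Protocol 5.6.i then says: "The design effect due to provider is then 1+9*r, where r is our assumed provider intra-class correlation". It continues: "If we assume that r=0.05, then the design effect is 1.45, and the effective sample is 1379". It also gives an effective sample of 1835 at r = 0.01 and a design effect of 1.9 at r = 0.1.

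The SAP (Sample Size and Power Considerations) carries the same factor, "so the design effect for an ICC of 0.05 is 1.45", and the 1835. The figure 1379 and the r = 0.1 case are in the protocol only.

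On the Hypothesis 1 model, protocol 5.6.a says: "Including a random intercept for provider, and correlated residuals within patient, should account for the nesting". The SAP agrees: "the models will include a random intercept for provider and correlated residuals within patient". Neither has a provider-by-group random term.

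For Hypothesis 2 the SAP makes no provider adjustment: "then our sample of 2000 provides 80% power to detect a common odds ratio of 1.29". Yet that model is also specified as "including random intercepts for providers and fixed effects for sites".

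**The concern.** The factor 1 + (m − 1)r is the variance inflation when a whole provider is assigned to one arm, because the provider effect then sits entirely on one side of the comparison. With both arms inside each provider, that effect is shared and mostly drops out. The documents do not describe the inflation as deliberately cautious. Protocol 5.6.i applies the word conservative to the value r = 0.1, not to the formula. Nor do they assume that the treatment effect varies between providers, which is the one mechanism that could bring inflation back.

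At stake is the stated power, not the validity of the trial. There are three consequences:

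- The plan's dependence of power on the ICC runs the wrong way.
- The SAP tests Hypothesis 1 at two-sided 2.5% but repeats the 82% and 92% that the protocol gives at 5%. Correcting alpha while keeping 1.45 would produce a shortfall that is not real.
- Hypotheses 1 and 2 treat provider clustering differently, and no reason is given.

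**Working it through.** **Inputs.** N = 2000; 200 providers with m = 10 patients; r = 0.01, 0.05, 0.10; 30% versus 35%; five visits; within-patient correlation 0.4; 20% loss spread evenly over time (SAP, Sample Size and Power Considerations; protocol 5.6.i). Alpha is two-sided 2.5% in the SAP and 5% in the protocol. The allocation ratio is not stated; 1:1 is assumed.

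**1. The plan's factors reproduce.** 1 + 9 × 0.05 = 1.45 and 2000/1.45 = 1379. 1 + 9 × 0.01 = 1.09 and 2000/1.09 = 1835. 1 + 9 × 0.10 = 1.90 and 2000/1.90 = 1053. The sums are right; the question is the formula.

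**2. The factor under this design.** Write the outcome variance as σ², with rσ² between providers. Within one provider with m/2 patients per arm, the rσ² part is common to both arm means, so the variance of their difference is 4σ²(1 − r)/m. Independent patients would give 4σ²/m. The ratio is 1 − r, and effective N is 2000/(1 − r): 2020, 2105 and 2222.

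**3. Numerical checks** (variance relative to independent patients):

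| Setting | r = 0.01 | r = 0.05 | r = 0.10 |
|---|---|---|---|
| Generalized least squares (GLS), permuted blocks within provider | 0.991 | 0.953 | 0.904 |
| Same, very unequal provider sizes | 0.991 | 0.953 | 0.906 |
| Simulated binary data, 5 per arm per provider | 1.00 | 0.94 | 0.90 |
| Simulated binary data, whole providers randomized | 1.09 | 1.44 | 1.90 |

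Only the last row matches the plan.

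**4. Power.** The contrast is the visit-averaged difference. A patient with k visits contributes information k/(1 + 0.4(k − 1)) under compound symmetry (CS) and (k − 0.4(k − 2))/1.4 under AR(1), in units of one visit. Two even-loss patterns were used, with 96/92/88/84/80% or 100/95/90/85/80% observed at the five visits. Average information per patient I is then 1.775 or 1.834 (CS) and 2.434 or 2.500 (AR(1)). With variance factor f,

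SE² = (0.30 × 0.70 + 0.35 × 0.65) × f/(1000 × I) = 0.4375f/(1000I),

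and power = Φ(0.05/SE − 2.2414) at two-sided 2.5%.

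Example, CS, I = 1.775:
- f = 1: SE = 0.01570, z = 3.185 − 2.241 = 0.943, power 82.7%.
- f = 1.45: SE = 0.01891, z = 2.645 − 2.241 = 0.403, power 65.7%.

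Results at two-sided 2.5%, ranges over the two loss patterns:

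| | r = 0.01 | r = 0.05 | r = 0.10 |
|---|---|---|---|
| CS, 1 − r | 83–84% | 85–86% | 87–88% |
| CS, 1 + 9r | 79–81% | 66–67% | 53–54% |
| AR(1), 1 − r | 93–94% | 94–95% | 95–96% |
| AR(1), 1 + 9r | 91–92% | 80–82% | 68–69% |

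At f = 1: CS 83–84%, AR(1) 93–94%. With alpha held at 5% and r = 0.05, the factor alone moves CS power from 75–77% to 90–91%.

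**5. The plan's 82% and 92%.** At the plan's own setting (5%, factor 1.45) this method gives 75–77% and 87–88% with loss, and 79% and 91% without. A closely similar two-proportion calculation reaches 82.3% and 92.2% with 25% versus 30%, two-sided 5% and no dropout. The method behind the stated figures is therefore not known.

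**The case against.** **It does no harm.** The error is conservative, N = 2000 was fixed on it, and no analysis depends on it. This is correct, and it limits the weight of the point to the accuracy of the stated power.

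**1 − r is a best case.** The intervention acts through prescribers. Protocol 5.2 expects variability in how results are used, and 5.6.a plans interactions of group with provider characteristics. If the treatment effect varies across providers with SD s, the factor is (1 − r) + (m/4)s²/σ². At r = 0.05, m = 10 and single-visit σ² = 0.325 × 0.675 = 0.219, an SD of 5, 10 or 15 points gives about 0.98, 1.06 and 1.21. On the visit-averaged scale (σ² × 0.52 under CS) it gives about 1.00, 1.17 and 1.44. Returning to 1.45 needs about 20 points (single visit) or 15 points (visit-averaged), three to four times the 5-point effect. This does not rescue 1 + 9r, which contains no such variance. It does mean that the assumption must be written down: at f = 1.17 the formula above gives CS power of about 76–77%.

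**More than 80% depends on the loss pattern.** If 20% of patients gave no follow-up data at all, CS power at 2.5% would be 76.4% at a factor of 1 and 78.7% at 0.95. That is not loss spread evenly over time, as both documents assume, but the pattern used should be stated.

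**The contrast is assumed.** The model has group-by-time terms, and neither document says that the Hypothesis 1 test is the visit-averaged difference. A single-visit approximation to the week-24 comparison (1600 patients, factor 1, 2.5%) has power of about 46%. The restated figures must name their contrast.

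**Hypothesis 2 is right to use all 2000.** By the same reasoning it is; only the explanation is missing.

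**Conclusion.** The point holds. The formula does not fit the documented randomization and model, so 1.45, 1379, 1835 and 1.9 are wrong as written, in the conservative direction. The discrepancy is largest at the higher ICCs: at 0.05 the factor should be about 0.95 rather than 1.45, a difference of 18 to 20 percentage points of CS power at two-sided 2.5%. The claim of more than 80% power for a 5-point effect survives the joint correction of factor and alpha, given 1:1 allocation, a common effect across providers, the visit-averaged contrast, and even loss reaching 20% by week 24.

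One related claim does not survive, for a different reason. Power above 90% at an ICC of 0.01 under either covariance structure is about met under CS at 5% with the corrected factor (89–90% with loss, 91.5% without), but is 83–84% at 2.5%. That shortfall comes from alpha, not from the design effect.

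**What to change.** Delete 1 + 9r and the effective sample sizes from the SAP power section and protocol 5.6.i. Replacement text could read: *Patients are randomized in permuted blocks within provider. Assuming no provider-by-treatment variance, the provider ICC does not inflate the variance of the group contrast, and power is computed from N = 2000.* If some provider-by-treatment variance is assumed, give its size and the resulting inflation.

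In the same edit:
- Restate Hypothesis 1 power at two-sided 2.5% for 30% versus 35%: about 83–84% (CS) and 93–94% (AR(1)) at a factor of 1. Name the visit-averaged contrast and the loss pattern.
- State that power above 90% is not reached under CS at 2.5%.
- Say in one sentence how provider clustering is handled for Hypotheses 1 and 2.

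The cost is wording and one recalculation. Patients, data, models and tests are unchanged.

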5.4 Inclusion/Exclusion Criteria

A total of 2000 men and women will be randomized. To reach this number, up to 250 subjects per site or a total of about 3000 subjects will be consented and screened.

Veteran subjects

Patient Inclusion Criteria. a) age 18 to 80 years, inclusive; b) PHQ-9 score \geq 10 and a presumptive diagnosis of MDD per the prescriber; c) at least one prior treatment exposure for MDD (psychotherapy or antidepressant); d) intent to start treatment of the MDD with an antidepressant (simple dose increases will not be considered inclusionary), and e) willingness to provide signed, informed consent to participate in the study.

Patient Exclusion Criteria. a) current serious co-occurring psychiatric illness (i.e., schizophrenia, bipolar disorder, psychotic major depression, borderline or antisocial personality disorder, eating disorder; b) active alcohol or other drug use disorder; c) current use of an antipsychotic medication, methadone, buprenorphine, or naltrexone (depot or oral); d) augmentation therapy (e.g., use of two or more antidepressants at the time of randomization), (trazodone at a dosage \leq 150 mg/day will not be considered augmentation and thus allowed); e) patients requiring urgent care or inpatient hospitalization at the time of consent; or f) currently incarcerated.

Prescribers

There is no limit on the number of prescribers that can be enrolled at each site. Sites will be encouraged to consent any prescriber who is interested in participating in the study.

Inclusion Criteria: Capacity to prescribe Exclusion Criteria: None

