Dropout and Missing Data. We anticipate that there will be dropout from the study as well as intermittent missing data, in particular for the patient outcome responses of Hypothesis #1, while some Veterans may not receive an antidepressant prescription in the 30-days post-randomization for Hypothesis #2. The mixed-effects models described above for Hypothesis #1 make use of all available responses, can accommodate the heterogeneity of response times caused by intermittent missing data, and provides valid estimates and hypothesis tests under an assumption of ignorable missingness. To assess the sensitivity of our conclusions to this assumption, we will extend the mixed-effects models to consider inverse probability-weighted selection models and pattern mixture models [22]. We will perform these analyses under a range of different prediction models and assess the sensitivity of the results. For Hypothesis #2 we will use a multiple imputation approach. [32-33]

Secondary Hypotheses.

Secondary Responses (Hypothesis #3). We will compare the intervention groups on their repeated depression response outcomes using mixed effects logistic regression models, as described for primary Hypothesis #1. For the PHQ-9 summary score of depression severity, we will use mixed-effects linear models.

We will use generalized linear regression models to compare the groups on side effect rate, treatment adherence rate, and functional improvement. Regression models will include random effects to accommodate correlations due to nesting of patients within providers, and repeated measures (where necessary).

Rationale for amendments made– Number of outpatient visits was removed from the secondary outcomes as there are no standards for an acceptable frequency of outpatient visits, particularly when comparing specialty mental health care and primary care.

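### The Hypothesis #2 power statement assumes a medication colour for all 2000 randomised patients and was not updated for the 30-day outcome, for which the SAP expects some patients to have no prescription

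*SAP*

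**What the plan says.** Four places bear on this point.

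- **SAP, Sample Size and Power Considerations.** On the significance level: "We have two primary hypotheses, so we will test each at a 2.5% significance level, using two-sided tests". On the colour distribution for Hypothesis #2: "Assuming that the overall proportions in the sample are approximately 40%/40%/20% for green/yellow/red, respectively". On the result: "our sample of 2000 provides 80% power to detect a common odds ratio of 1.29 under a proportional odds model". The outcome powered here is the colour "of the initial prescription made during the intervention period". The paragraph just before, on Hypothesis #1, allows for 20% loss to follow-up. The Hypothesis #2 paragraph contains no allowance.
- **SAP, analysis text for Hypothesis #2.** "The primary outcome for Hypothesis #2 will be the ordinal variable corresponding to prescriptions written in the first 30 days after randomization". The rationale near the start of the SAP records that the Executive Committee agreed the 30-day window on 8/16/21.
- **SAP, Dropout and Missing Data.** "some Veterans may not receive an antidepressant prescription in the 30-days post-randomization for Hypothesis #2". Multiple imputation is planned for this hypothesis. No expected rate is given and no imputation variables are named.
- **Protocol 5.4.** "A total of 2000 men and women will be randomized". The 2000 in the power statement is thus the full randomised number.

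**The concern.** The power figure uses every randomised patient, while the SAP itself says that some may have no observed outcome. If the calculation has no margin, any patient without a colour takes the true power below the stated value. A likely source can be seen in the text: the outcome was narrowed to 30 days, but the power paragraph still refers to the intervention period, and fewer patients can have a prescription within 30 days than within 24 weeks.

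Hypothesis #2 is one of two primary hypotheses. If its result were null, readers would judge it against a detectable effect that is somewhat too favourable.

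**Working it through.** **Inputs**

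- Two-sided significance level 0.025, so z = 2.2414 (SAP, Sample Size and Power Considerations).
- 80% power, so z = 0.8416 (same paragraph).
- Overall colour proportions 0.40 / 0.40 / 0.20 (same paragraph).
- N = 2000 (same paragraph; Protocol 5.4).
- Odds ratio 1.29, so ln(1.29) = 0.2546.
- Allocation 1:1. This is an assumption. The Protocol says "The randomization will be based on a permuted blocks approach, with (slightly) varying block sizes" and states no ratio.

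**Formula** (Whitehead, proportional odds, 1:1)

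V = (N/12) × (1 − Σp³)

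power = Φ(ln OR × √V − 2.2414)

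detectable OR = exp[(2.2414 + 0.8416)/√V]

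**Step 1: reproduce the stated figure.**

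- Σp³ = 0.064 + 0.064 + 0.008 = 0.136, so 1 − Σp³ = 0.864.
- V = (2000/12) × 0.864 = 144, so √V = 12.
- Power at 1.29 = Φ(0.2546 × 12 − 2.2414) = Φ(0.814) = 79.2%.
- Detectable OR = exp(3.0830/12) = 1.293.
- Number of observed outcomes for a full 80% at 1.29: 12 × 3.0830² / (0.2546² × 0.864) = 2036.

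The stated figure therefore reproduces, within rounding, with all 2000 observed. A two-sided 5% level gives 86.3%, which does not match. Reading 40/40/20 as one arm's proportions instead of the overall ones gives 78.8% to 79.6%. A simulation of the tie-corrected Wilcoxon test (20,000 runs) gives 79.0%.

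**Step 2: allow for patients without a colour.** Let d be the share without one. The documents give no value, so the range is assumed. With nothing recovered by imputation, replace N by 2000 × (1 − d):

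| d | Patients with a colour | Power at OR 1.29 | Detectable OR, 80% power |
|---|---|---|---|
| 0% | 2000 | 79.2% | 1.293 |
| 2% | 1960 | 78.3% | 1.296 |
| 5% | 1900 | 76.9% | 1.302 |
| 10% | 1800 | 74.5% | 1.311 |
| 20% | 1600 | 68.9% | 1.333 |

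Simulated power at 1900, 1800 and 1600 is 77.2%, 74.1% and 68.9%. Power drops below 78%, that is, more than 2 points under the stated 80%, once d exceeds about 2.7%.

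**Step 3: allow for imputation.** If a fraction r of the lost information is recovered, the effective number is 2000 × (1 − d + d·r). At r = 0.5, power is 78.1% for d = 5%, 76.9% for d = 10% and 74.5% for d = 20%. At r = 1 it is 79.2% for any d, which is the ceiling.

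**The case against.** The best counter-argument is that the share without a prescription may be very small.

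- Eligibility requires an intent to start an antidepressant (Protocol 5.4), and the provider records the planned drug at referral (5.5.a).
- In the delayed arm the drug can be started the same day. In the intervention arm results usually arrive in 2-3 business days, with up to four more if delayed (5.2).
- Intervention patients are reminded to call if they have not heard within 10 business days (5.1).
- The coordinator checks the chart for a prescription, or a note explaining its absence, by the 1-month blood draw (6.0).
- Medication data come from the health record, so a missed follow-up call does not lose a colour. The 20% loss assumed for Hypothesis #1 is therefore not a guide to the rate here.

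All of this stands, and it limits the size. It does not remove the gap, because the SAP foresees such patients and the calculation has no margin to absorb them.

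The second argument is imputation. A reader might infer that imputing a colour adds no information, so that the effective sample is exactly the number with a prescription. That is the worst case. The planned antidepressant is recorded before randomisation, can be coloured from the test report, and in the delayed arm is the drug to be started (5.5, Visit 1). It could recover some information, mainly in that arm. The SAP does not name it for the imputation model, however, and it says less about choices made after the results are seen.

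Third, the change is small. An odds ratio of 1.30 to 1.33 in place of 1.29 is comparable with the looseness of the colour proportions: with all 2000 observed, 50/35/15 gives 1 − Σp³ = 0.829 and a detectable odds ratio of 1.30, and 60/30/10 gives 0.756 and 1.32. This is a fair reason to rank the point as minor.

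**Conclusion.** The point holds as a minor one. The stated 80% power at an odds ratio of 1.29 is correct arithmetic for 2000 observed colours, and for nothing less. It does not match the 30-day outcome that the SAP now specifies, for which the SAP expects some outcomes to be absent. The stated power is therefore somewhat too favourable.

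The size depends on a share that the documents do not give. Between 2% and 20% without a colour, power at 1.29 is about 78% to 69% and the detectable odds ratio is 1.30 to 1.33, assuming 1:1 allocation and no recovery by imputation. Partial recovery would narrow this loss, and full recovery would only restore 79.2%.

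Two stronger readings are not supported. A reader might infer that the power of Hypothesis #2 has been shown to fall well short, say to 74% or 69%. Those figures need 10% or 20% without a prescription, and the documents contain no such rate and several reasons to expect fewer. A reader might also apply the provider design effect of 1.45 from Hypothesis #1. Randomisation is within provider (Protocol 5.2), so that factor does not carry over directly, and this point does not rely on it.

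**What to change.** In the SAP's Sample Size and Power Considerations:

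1. Define the powered outcome for Hypothesis #2 as the colour of prescriptions in the first 30 days after randomisation, in line with the analysis text.
2. State the share of patients expected to have no such prescription, with its basis.
3. Restate the detectable odds ratio at 80% power, or the power at 1.29, for the expected number with a colour. For example, the detectable odds ratio is about 1.30 at 5% without a colour and 1.31 at 10%, with 1.33 at 20% as a worst case.

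If the sponsor wishes to claim recovery through imputation, the auxiliary variables relied on should be named. The cost is one restated, slightly less favourable figure. Neither the design nor the analysis changes.
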